12.3.1 Overall response

Response will be monitored closely in patients using the method of Thall et al (1995). Denote the probability of overall response by P_E . We assume $P_E \sim \text{beta}(1, 1)$. We will stop the trial of this treatment if at any point $\text{Pr}(P_E < 0.5 \mid \text{data}) > 0.98$. That is, we will stop the treatment of this combination if, at any time during the study, we determine that there is more than 98% chance that the response rate is less than 50%. The trial will be stopped if (the number of response observed / among number of patients) $\leq 1/10, 2/12, 3/15, 4/18, 5/21, \text{ and } 6/24$.

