12.3.2 Toxicity

Toxicity will be monitored closely using the method of Thall et al (1995). Denote the probability of toxicity by θ_E , where toxicity is defined as DLTs. We assume $\theta_E \sim \text{beta}(0.6, 1.4)$. We will stop the trial if at any point $\Pr(\theta_E > 0.30 \mid \text{data}) > 0.9$. That is, we will stop the trial of this combination therapy if, at any time during the study, we determine that there is more than 90% chance that the toxicity rate is more than 30%. The trial will be stopped if (the number of toxicity observed / among number of patients) $\geq 6/11, 7/14, 8/16, 9/19, 10/22$ and $11/24$.

Table 1 presents operating characteristics for the study design.

Table 1: Operating characteristics

Response rate	Toxicity rate	Probability of early stopping	Average number of patients
0.2	0.1	0.862	15.01
	0.2	0.864	14.94
	0.3	0.884	14.48
	0.4	0.929	13.37
	0.5	0.974	11.95
0.3	0.1	0.497	20.31
	0.2	0.508	20.14
	0.3	0.579	19.11
	0.4	0.743	16.64
	0.5	0.907	13.62
0.4	0.1	0.175	24.02
	0.2	0.192	23.79
	0.3	0.309	23.33
	0.4	0.577	18.88
	0.5	0.847	14.72
0.5	0.1	0.038	25.54
	0.2	0.058	25.29
	0.3	0.194	23.65
	0.4	0.507	19.79
	0.5	0.822	15.16
0.6	0.1	0.005	25.93
	0.2	0.026	25.67
	0.3	0.167	23.99
	0.4	0.49	20.02
	0.5	0.816	15.27

MultcLean V1.2 developed in the Department of Biostatistics MDACC was used to calculate the stopping boundaries for futility and toxicity monitoring rules.

Treatment with AC220 + 5-azacytidine (Cohort 2A-FLT3-ITD)

Up to 50 newly diagnosed patients (including patients treated at the same dose in phase I) and up to 50 previously treated patients (including patients treated at the same dose in phase I) will be treated with AC220 + 5-azacytidine. The analysis for the two groups of patients will be completed separately.

The study will monitor futility and safety for each patient group and the monitoring will begin when 15 patients have been enrolled in that group, and thereafter by a cohort of 5 patients. The trial in one group will be stopped early if at any time point the data in that group suggest

$$\Pr(P_E < 0.5 \mid \text{data}) > 0.98 \text{ or}$$

$$\Pr(\theta_E > 0.30 \mid \text{data}) > 0.9$$

Where P_E denote the response rate for experimental treatment, and θ_E denotes the toxicity rate for the experimental treatment combination. Assume $P_E \sim$ prior beta(1,1) and $\theta_E \sim$ prior beta(0.6, 1.4).

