That is, the trial in one group will be stopped early for futility if the data for that group indicate that there is more than 98% probability that the response rate is less than 50% or the trial for one group will be stopped early for toxicity if the data that group indicate that there is more than 90% probability that the toxicity rate (i.e. DLT rate) is more than 30%.

The corresponding stopping boundaries for futility is: the trial in one group will be stopped early if (the number of response observed / among number of patients) in that group $\leq 3/15, 5/20, 7/25, 9/30, 11/35, 13/40$ and $15/45$.

The corresponding stopping boundaries for toxicity is: The trial will be stopped early in one group if (the number of patients experienced DLTs / among number of patients) in that group $\geq 8/15, 9/20, 11/25, 13/30, 15/35, 16/40$ and $18/45$.

Table 2 presents the operating characteristics for the above design.

Table 2: OCs for the design for cohort 2A with AC220 + 5-AZA

Response rate	Toxicity rate	Probability of early stopping	Average number of patients
0.2	0.1	0.993	18.6
	0.2	0.993	18.6

	0.3	0.994	18.2
	0.4	0.998	17.4
	0.5	1	16.2
0.35	0.1	0.584	35.8
	0.2	0.59	35.5
	0.3	0.669	32.9
	0.4	0.865	26
	0.5	0.983	19.4
0.5	0.1	0.055	48.6
	0.2	0.069	48.2
	0.3	0.247	43.7
	0.4	0.694	31.7
	0.5	0.96	21
0.65	0.1	0.009	50
	0.2	0.016	49.6
	0.3	0.204	44.8
	0.4	0.676	32.4
	0.5	0.958	21.2

If the trial in one group continues until 50 patients are evaluated, and assuming the overall response rate is 50%, then the 95% credible interval for overall response rate would be (0.36, 0.64).

B: Cohort 2B – FLT3-WT

Up to 50 patients FLT3-WT will be treated AC220 + 5-azacytidine. The primary objective is to determine the over response. In a recent phase 2 study, we observed a single agent AC220 response of 30% in a salvage setting. We would like to have a 15% improvement (i.e. response rate of 45%) under the combination treatment in this study.

The study will also monitor futility and safety for this cohort. Monitoring will begin when 15 patients have been enrolled in that group, and thereafter by a cohort of 5 patients. The trial in this cohort will be stopped early if at any time point the data in that group suggest

$$\Pr(P_E < 0.15 + P_S \mid \text{data}) > 0.98 \text{ or}$$

$$\Pr(\theta_E > 0.30 \mid \text{data}) > 0.9$$

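### Cytarabine arm: the written any-time stopping criterion stops sooner than the printed boundaries and Table 1, and no look schedule is stated

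*Combined protocol and SAP*

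**What the plan says.** Section 12.3.1 puts a beta(1,1) prior on the response rate P_E. It stops the cytarabine arm if, "at any time during the study, we determine that there is more than 98% chance that the response rate is less than 50" per cent. The futility boundaries printed for this are at most "1/10, 2/12, 3/15, 4/18, 5/21" and 6/24 responses.

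Section 12.3.2 puts a beta(0.6, 1.4) prior on the DLT rate. It stops the arm if, "at any time during the study, we determine that there is more than 90% chance that the toxicity rate is more than 30" per cent. The printed toxicity boundaries are at least "6/11, 7/14, 8/16, 9/19, 10/22" and 11/24 DLTs. The section then says "Table 1 presents operating characteristics for the study design", and that the MultcLean program "was used to calculate the stopping boundaries for futility and toxicity monitoring rules".

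The arm has 26 patients, including the six treated at the MTD in phase I (Section 12.3). No first look, minimum number or interval is given for it. For the azacitidine groups of Cohort 2A, which use the same priors and cut-offs, the text says "the monitoring will begin when 15 patients have been enrolled in that group, and thereafter by a cohort of 5 patients" and prints futility boundaries "3/15, 5/20, 7/25, 9/30, 11/35, 13/40" and 15/45. Cohort 2B states the same look schedule.

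**The concern.** A criterion that applies at any time, a list of boundaries and a table of operating characteristics should be three descriptions of one rule. If the list omits counts at which the criterion is already met, a monitor who follows the sentence stops the arm where a monitor who follows the list goes on enrolling. If Table 1 was computed from the list, it does not give the properties of the rule in the text.

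The missing look schedule makes this worse. Six phase I patients count toward the 26, and the futility criterion can be met with five patients, yet the first listed futility boundary is at ten.

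**Working it through.** **Inputs** (Section 12.3 with 12.3.1 and 12.3.2): N = 26; priors beta(1,1) and beta(0.6, 1.4); thresholds 0.5 and 0.30; cut-offs 0.98 and 0.90. Response and toxicity are taken as independent.

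**Posteriors.** With x responses in n patients, Pr(P_E < 0.5) is the beta(1+x, 1+n−x) distribution function at 0.5, which equals Pr(Bin(n+1, 0.5) ≥ x+1). With y DLTs, Pr(θ_E > 0.30) is the upper tail of beta(0.6+y, 1.4+n−y) at 0.30. Two hand checks:
- 0/5 responses: 1 − 1/64 = 0.9844.
- 2/11 responses: 1 − (1 + 12 + 66)/4096 = 0.9807.

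**Printed pairs.** Each meets its criterion, with futility posteriors of 0.989 to 0.994 and toxicity posteriors of 0.924 to 0.940.

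**Where the criterion is met but the lists, read as steps, continue:**
- Responses: 2/11 (0.9807), 3/14 (0.9824), 4/17 (0.9846), 5/20 (0.9867), 6/22 (0.9827), 7/25 (0.9855). Before the tenth patient: 0/5 (0.9844) and 1/8 (0.9805).
- DLTs: 6/12 (0.9051), 8/17 (0.9141), 9/20 (0.9059), 11/25 (0.9180).

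**Reproducing Table 1.** I used an exact forward recursion over (responses, DLTs). At each look the probability in the stopping region is removed. Its sum is the stopping probability, and average N is Σ n × (probability removed at n) + 26 × (probability remaining). The printed lists were applied as steps: futility counts carried forward, each toxicity count used up to its listed n, after every patient from n = 10. This gives all 25 stopping probabilities within 0.001 and 24 of 25 average Ns to rounding. The exception is response 0.4, toxicity 0.3, printed 23.33 and computed 22.33. The start at ten is identified by average N at 0.5/0.5, printed 15.16: starting at 9, 10 or 11 gives 14.91, 15.16 or 15.55.

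**The written criterion, every patient from n = 10:**

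| Response / toxicity | Table 1, stop | Written criterion, stop |
|---|---|---|
| 0.2 / 0.1 | 0.862 | 0.924 |
| 0.3 / 0.1 | 0.497 (average N 20.31) | 0.618 (average N 18.9) |
| 0.4 / 0.1 | 0.175 | 0.254 |
| 0.5 / 0.1 | 0.038 | 0.063 |
| 0.5 / 0.3 | 0.194 | 0.248 |

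The criterion's figure is higher in all 25 rows, by 0.005 to 0.121. Its stopping region contains that of the lists. So at 0.3/0.1 about 12% of trials (0.618 − 0.497 = 0.121) run to 26 although the written rule had said stop.

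**Other look schedules.** From the first patient, the criterion gives 0.647 at 0.3/0.1, 0.101 at 0.5/0.1 and 0.351 at 0.5/0.3. At 15, 20 and 25 it gives 0.562 at 0.3/0.1 and 0.037 at 0.5/0.1.

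**Phase I entry condition.** Requiring at most one DLT in the first six patients barely moves the low-toxicity rows: 0.617 at 0.3/0.1 and 0.063 at 0.5/0.1. At 0.5/0.4 the criterion gives 0.267 and the lists 0.199.

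**Comparison within the plan.** The azacitidine lists reproduce from the written criterion at all seven looks. So 5/20 responses or 9/20 DLTs stops an azacitidine group, while the cytarabine lists, read as steps, continue at both counts under an identical criterion.

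**The case against.** The best defence is that nothing printed is miscalculated. Each of the twelve printed pairs is the criterion's exact boundary at its own sample size. If futility is examined only at its six listed sizes and toxicity only at its six, all 25 stopping probabilities in Table 1 reproduce within 0.001. On that reading the counts missed by the lists lie at sample sizes where nobody looks, and the size of any gap depends on a schedule the plan does not give.

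The first statement is true, and so is the dependence on schedule. The listed-sizes reading nevertheless fails on three points:
- It contradicts the instruction to stop at any time.
- It needs futility and toxicity to be examined on different sets of patients. Applying both criteria at every listed size gives 0.565 at 0.3/0.1, not 0.497.
- It misses the printed average N by up to 0.48. At 0.5/0.5 it gives 15.64 against 15.16, which the step reading matches.

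**Conclusion.** The concern holds. Table 1 belongs to the printed lists, applied as steps after every patient from the tenth, and the text does not say so. It does not describe the written criterion, which stops more often: up to 12.1 percentage points more with a first look at ten patients, and up to 18.5 points more with no minimum. Table 1 therefore understates early stopping both when response is poor and at the 50% target.

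The exact gap rests on independent outcomes and on an assumed first look, because the plan gives none. That the two rules differ under any-time monitoring does not rest on those assumptions, since it follows from the posteriors alone.

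One possible cause, which is an assumption because the plan states no such prior for this arm, is comparison with an uncertain standard rate instead of a fixed value. Beta(50,50) for response and beta(30,70) for toxicity reproduce both lists from n = 10 to 24. The conclusion does not depend on this.

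**What to change.** State the first look and the look interval for the cytarabine arm, and make the criteria, both lists and Table 1 describe one rule. There are two ways:

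1. **The written criterion governs.** Print its boundaries at each look and recompute Table 1. From the tenth patient, in step notation, these are at most 1/10, 2/11, 3/14, 4/17, 5/20, 6/22 and 7/25 responses, and at least 6/12, 7/14, 8/17, 9/20, 10/22 and 11/25 DLTs. Stopping at 0.5/0.1 then rises from 0.038 to 0.063. On the azacitidine schedule (15, 20, 25) it would be 0.037, with 0.562 and average N 21.7 at 0.3/0.1.
2. **The printed lists govern.** Say that they apply as steps after every patient from the tenth, state any standard-rate prior that produced them, and replace the fixed-threshold any-time wording. Table 1 then stands apart from one cell.

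In the same rerun, correct the average N at 0.4/0.3 in Table 1 (22.33, not 23.33). Also recheck the Table 2 stopping probability at 0.65/0.1, printed 0.009 and computed 0.0009.

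The cost is text and one software rerun. Sample size does not change.

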12.3.2 Toxicity

Toxicity will be monitored closely using the method of Thall et al (1995). Denote the probability of toxicity by θ_E , where toxicity is defined as DLTs. We assume $\theta_E \sim \text{beta}(0.6, 1.4)$. We will stop the trial if at any point $\Pr(\theta_E > 0.30 \mid \text{data}) > 0.9$. That is, we will stop the trial of this combination therapy if, at any time during the study, we determine that there is more than 90% chance that the toxicity rate is more than 30%. The trial will be stopped if (the number of toxicity observed / among number of patients) $\geq 6/11, 7/14, 8/16, 9/19, 10/22$ and $11/24$.

Table 1 presents operating characteristics for the study design.

Table 1: Operating characteristics

Response rate	Toxicity rate	Probability of early stopping	Average number of patients
0.2	0.1	0.862	15.01
	0.2	0.864	14.94
	0.3	0.884	14.48
	0.4	0.929	13.37
	0.5	0.974	11.95
0.3	0.1	0.497	20.31
	0.2	0.508	20.14
	0.3	0.579	19.11
	0.4	0.743	16.64
	0.5	0.907	13.62
0.4	0.1	0.175	24.02
	0.2	0.192	23.79
	0.3	0.309	23.33
	0.4	0.577	18.88
	0.5	0.847	14.72
0.5	0.1	0.038	25.54
	0.2	0.058	25.29
	0.3	0.194	23.65
	0.4	0.507	19.79
	0.5	0.822	15.16
0.6	0.1	0.005	25.93
	0.2	0.026	25.67
	0.3	0.167	23.99
	0.4	0.49	20.02
	0.5	0.816	15.27

MultcLean V1.2 developed in the Department of Biostatistics MDACC was used to calculate the stopping boundaries for futility and toxicity monitoring rules.

Treatment with AC220 + 5-azacytidine (Cohort 2A-FLT3-ITD)

Up to 50 newly diagnosed patients (including patients treated at the same dose in phase I) and up to 50 previously treated patients (including patients treated at the same dose in phase I) will be treated with AC220 + 5-azacytidine. The analysis for the two groups of patients will be completed separately.

The study will monitor futility and safety for each patient group and the monitoring will begin when 15 patients have been enrolled in that group, and thereafter by a cohort of 5 patients. The trial in one group will be stopped early if at any time point the data in that group suggest

$$\Pr(P_E < 0.5 \mid \text{data}) > 0.98 \text{ or}$$

$$\Pr(\theta_E > 0.30 \mid \text{data}) > 0.9$$

Where P_E denote the response rate for experimental treatment, and θ_E denotes the toxicity rate for the experimental treatment combination. Assume $P_E \sim$ prior beta(1,1) and $\theta_E \sim$ prior beta(0.6, 1.4).

That is, the trial in one group will be stopped early for futility if the data for that group indicate that there is more than 98% probability that the response rate is less than 50% or the trial for one group will be stopped early for toxicity if the data that group indicate that there is more than 90% probability that the toxicity rate (i.e. DLT rate) is more than 30%.

The corresponding stopping boundaries for futility is: the trial in one group will be stopped early if (the number of response observed / among number of patients) in that group $\leq 3/15, 5/20, 7/25, 9/30, 11/35, 13/40$ and $15/45$.

The corresponding stopping boundaries for toxicity is: The trial will be stopped early in one group if (the number of patients experienced DLTs / among number of patients) in that group $\geq 8/15, 9/20, 11/25, 13/30, 15/35, 16/40$ and $18/45$.

Table 2 presents the operating characteristics for the above design.

Table 2: OCs for the design for cohort 2A with AC220 + 5-AZA

Response rate	Toxicity rate	Probability of early stopping	Average number of patients
0.2	0.1	0.993	18.6
	0.2	0.993	18.6

	0.3	0.994	18.2
	0.4	0.998	17.4
	0.5	1	16.2
0.35	0.1	0.584	35.8
	0.2	0.59	35.5
	0.3	0.669	32.9
	0.4	0.865	26
	0.5	0.983	19.4
0.5	0.1	0.055	48.6
	0.2	0.069	48.2
	0.3	0.247	43.7
	0.4	0.694	31.7
	0.5	0.96	21
0.65	0.1	0.009	50
	0.2	0.016	49.6
	0.3	0.204	44.8
	0.4	0.676	32.4
	0.5	0.958	21.2

If the trial in one group continues until 50 patients are evaluated, and assuming the overall response rate is 50%, then the 95% credible interval for overall response rate would be (0.36, 0.64).

B: Cohort 2B – FLT3-WT

Up to 50 patients FLT3-WT will be treated AC220 + 5-azacytidine. The primary objective is to determine the over response. In a recent phase 2 study, we observed a single agent AC220 response of 30% in a salvage setting. We would like to have a 15% improvement (i.e. response rate of 45%) under the combination treatment in this study.

The study will also monitor futility and safety for this cohort. Monitoring will begin when 15 patients have been enrolled in that group, and thereafter by a cohort of 5 patients. The trial in this cohort will be stopped early if at any time point the data in that group suggest

$$\Pr(P_E < 0.15 + P_S \mid \text{data}) > 0.98 \text{ or}$$

$$\Pr(\theta_E > 0.30 \mid \text{data}) > 0.9$$

Where P_E and P_S denote the response rate for experimental and standard treatment, respectively, and θ_E denotes the toxicity rate for the experimental treatment combination. Assume $P_E \sim$ prior beta(0.6, 1.4) and $\theta_E \sim$ prior beta(0.6, 1.4).

That is, the trial in this cohort will be stopped early for futility if the data indicate that there is more than 98% probability that the response rate is not improved by 15% or the trial will be stopped early for toxicity if the data indicate that there is more than 90% probability that the toxicity rate (i.e. DLT rate) is more than 30%. The corresponding stopping boundaries for futility is: the trial in this cohort will be stopped early if (the number of response observed / among number of patients) in this cohort $\leq 3/15, 4/20, 6/25, 8/30, 10/35, 11/40$ and $13/45$.

The corresponding stopping boundaries for toxicity is: The trial will be stopped early in this cohort if (the number of patients experienced DLTs / among number of patients) in this cohort $\geq 8/15, 9/20, 11/25, 13/30, 15/35, 16/40$ and $18/45$.

Table 3 presents the operating characteristics for the above design.

Table 3: OCs for the design for cohort 2B

Response rate	Toxicity rate	Probability of early stopping	Average number of patients
0.3	0.1	0.64	33
0.3	0.3	0.72	30.6
0.3	0.5	0.99	18.8
0.45	0.1	0.08	47.8
0.45	0.3	0.27	43
0.45	0.5	0.96	20.9
0.6	0.1	0.002	49.9
0.6	0.3	0.21	44.8
0.6	0.5	0.96	21.2

If the trial in one group continues until 50 patients are evaluated, and assuming the overall response rate is 45%, then the 95% credible interval for overall response rate would be (0.31, 0.58).

12.4 Analysis Plan:

For discrete or categorical data, descriptive statistics will include tabulations of frequencies. For continuous data, summary statistics including n, mean, standard deviation, median, minimum and maximum will be computed. The posterior response rate and its 95% credible intervals will be estimated.

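### In the three 50-patient AZA groups the first toxicity look comes at patient 15; optional looks at 5 and 10 under the plan's own rule would cost little

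*Combined protocol and SAP*

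**What the plan says.** For the two 2A AZA groups (Section 12.3, AC220 + 5-azacytidine), "monitoring will begin when 15 patients have been enrolled in that group, and thereafter by a cohort of 5 patients". The next sentence reads: "The trial in one group will be stopped early if at any time point the data in that group suggest", followed by the futility and toxicity criteria. Cohort 2B has the same schedule: "Monitoring will begin when 15 patients have been enrolled in that group, and thereafter by a cohort of 5 patients".

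The toxicity criterion is that "there is more than 90% probability that the toxicity rate (i.e. DLT rate) is more than 30" per cent, with a beta(0.6, 1.4) prior on the DLT rate. All three groups have the same printed limits: "8/15, 9/20, 11/25, 13/30, 15/35, 16/40" and then 18/45, stopping at or above each. Each group has at most 50 patients. The 2A AZA groups count phase I patients treated at the same dose; the 2B text does not say this.

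The only formal DLT check before patient 15 is in phase I (Sections 5.2.5.1 to 5.2.5.5 and 12.2). A dose level exceeds the MTD if 2 or more of 6 patients have a DLT, judged separately for each treatment arm.

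**The concern.** If the true DLT rate in one of these populations is well above 30%, up to 15 patients are treated before any rule specific to that group can respond. The posterior criterion could be met much sooner. Phase I clears a dose for the AZA arm as a whole on six patients, and six patients cannot stand in for three phase II groups. The question is how many patients an earlier look would spare, and how often it would stop a group whose toxicity is acceptable.

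**Working it through.** **Inputs (Section 12.3).** Prior beta(0.6, 1.4); stop if Pr(DLT rate > 0.30 | data) > 0.90; looks at 15, 20, ..., 45; maximum 50; printed futility limits of 3/15, 5/20, 7/25, 9/30, 11/35, 13/40, 15/45 (2A AZA) and 3/15, 4/20, 6/25, 8/30, 10/35, 11/40, 13/45 (2B).

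**1. The plan's limits.** With x DLTs in n patients the posterior is beta(0.6 + x, 1.4 + n − x), and the limit is the smallest x whose tail probability above 0.30 exceeds 0.90. At n = 15, 7 DLTs give 0.893 and 8 give 0.960, so the limit is 8. At n = 20, 8 give 0.807 and 9 give 0.906, so the limit is 9. All seven printed limits follow in this way.

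**2. The plan's tables.** Response and toxicity are taken as independent. An exact binomial recursion carries the joint counts from look to look and removes paths that meet either limit. If s(n) is the probability of stopping at look n, then P(stop) = Σ s(n) and E[N] = Σ n·s(n) + 50·(1 − Σ s(n)).

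- Table 2, response 0.5, toxicity 0.3: computed 0.247 / 43.7; printed 0.247 / 43.7.
- Table 2, response 0.65, toxicity 0.5: computed 0.958 / 21.2; printed 0.958 / 21.2.
- Table 3, response 0.45, toxicity 0.5: computed 0.961 / 20.9; printed 0.96 / 20.9.

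The other cells agree within tolerance. The largest gap is Table 2 at response 0.65, toxicity 0.1 (printed 0.009, computed 0.001, average N agreeing), and it does not affect this point. The tables therefore assume no look before 15.

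**3. The same rule at smaller n.** At n = 5, 3 DLTs give 0.875 and 4 give 0.975, so the limit is 4. At n = 10, 5 give 0.880 and 6 give 0.962, so the limit is 6.

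**4. Toxicity looks added at 5 and 10, futility looks unchanged** (2A AZA, response 0.65, no phase I patients carried over, outcomes known at once):

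| DLT rate | P(stop), plan | P(stop), added looks | E[N], plan | E[N], added looks | Patients saved |
|---|---|---|---|---|---|
| 0.2 | 1.6% | 2.3% | 49.6 | 49.2 | 0.4 |
| 0.3 | 20.4% | 22.2% | 44.8 | 43.6 | 1.3 |
| 0.4 | 67.6% | 68.7% | 32.4 | 30.1 | 2.2 |
| 0.5 | 95.8% | 96.0% | 21.2 | 17.8 | 3.5 |
| 0.6 | 99.9% | 99.9% | 16.6 | 11.4 | 5.2 |

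Savings are taken before rounding. As a hand check at a rate of 0.5, P(4 or more of 5) = 6/32 = 0.1875. The look at 10 adds 0.2197, so the chance of stopping by patient 10 goes from zero to 0.41. In 2B at response 0.45, E[N] falls from 20.9 to 17.5 at a DLT rate of 0.5, and from 43.0 to 41.8 at 0.3.

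**5. Phase I cover.** P(2 or more of 6) = 1 − (1 − p)⁶ − 6p(1 − p)⁵. At p = 0.5 this is 1 − 7/64 = 0.89. At 0.3, 0.4 and 0.6 it is 0.58, 0.77 and 0.96.

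**6. Carry-over.** The number of phase I patients entering each 2A group is not stated, so 0 to 6 is an assumed range. On the toxicity rule alone, given at most 1 DLT in the 6 phase I patients:

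| DLT rate | 0 carried over | 2 | 4 | 6 |
|---|---|---|---|---|
| 0.4 | 2.2 saved | 0.9 | 0.2 | 0 |
| 0.5 | 3.5 saved | 1.5 | 0.4 | 0 |
| 0.6 | 5.2 saved | 2.5 | 0.9 | 0 |

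With six carried over and at most one DLT among them, four more patients cannot bring the total to 6 by patient 10.

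**The case against.** The strongest reply is that this is a disclosed design choice with matching operating characteristics, and that phase I has already screened the dose. Much of that stands. The largest savings occur at DLT rates of 50% and 60%, where phase I would have tripped with probability 0.89 and 0.96. They also assume immediate outcomes. Under Section 5.2.5, DLT is judged over the first cycle and the hematologic criterion needs 6 weeks or more, so patients enrolled in the meantime reduce the gain.

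The reply does not close the gap. Phase I takes any FLT3 status (Section 4.1.2.2) and is judged per arm, so its six patients at the chosen dose may contribute few to a given group, and 2B is not said to receive any.

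Four stronger readings are tempting, and the documents do not support them:

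- **The plan contradicts itself on when the rule applies.** The phrase about any time point directly follows the stated schedule and reads naturally as any scheduled look. The limits and tables agree with that reading.
- **The LDAC group is monitored continuously and sets a precedent.** Its text does say "We will stop the trial if at any point", but its first printed toxicity limit is 6/11. It has no printed toxicity look at 5 or 10 either.
- **Continuing after 7 DLTs in 15 shows the look is too late.** That result comes from the 0.90 cut-off (posterior 0.893), and 7/15 would still not stop with the added looks.
- **Newly diagnosed patients go largely untested in phase I.** Section 4.1.2.1.4 admits untreated patients who are not candidates for intensive therapy. No count by prior treatment is given.

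**Conclusion.** The point holds as a late first toxicity look in three groups, and the added looks are an optional, low-cost improvement. The printed limits and tables are not in error. The benefit is material only when the DLT rate exceeds the plan's 30% limit: about 2 to 5 patients per group at rates of 40% to 60%, and little more than 1 at the limit itself. The price is 0.7 to 0.8 percentage points more stopping at a 20% DLT rate (1.6% to 2.3%) and 1.8 points at 30%.

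These figures assume independent response and toxicity, no phase I carry-over and immediate DLT outcomes. The saving falls towards zero as more phase I patients are carried into a group, and is smaller if accrual continues during DLT observation. The case is therefore clearest for 2B and for any 2A AZA group that starts with few phase I patients.

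**What to change.** For toxicity only, add looks at 5 DLT-evaluable patients (stop at 4 or more) and at 10 (stop at 6 or more) in each 2A AZA group and in 2B. Both limits come from the existing beta(0.6, 1.4) rule and 0.90 cut-off. Keep futility looks from 15. State that the any-time-point wording means the scheduled looks, state how many phase I patients count towards each group, and rerun Tables 2 and 3 on the new schedule.

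The cost is two more checks per group, recomputed tables and the small increase in stopping at acceptable DLT rates given above.
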